H2: Risks for Macrovascular Disease. We will compare NV and C participants on measures of arterial stiffness: peripheral systolic and diastolic BP (averaged over the two assessments), cfPWV, and AI.

H3: Markers of Chronic Kidney Disease (CKD). We will compare NV and C participants on the estimated Glomerular Filtration Rate (eGFR) and the microalbumin/creatinine ratio.

H4: Metabolic Outcomes: We will compare NV and C participants on measures of Glycosylated Hemoglobin (HbA1C), dyslipidemia (TC, LDL, HDL, TG), and the AST/ALT ratio.

H5: Immune/Inflammatory Markers: We will compare NV and C participants on immune/inflammatory markers [hsCRP, fibrinogen, interleukin 6 (IL-6), tumor necrosis factor alpha-receptor 2 (TNF-2), and insulin-like growth factor-1 (IGF-1 – free and total)].

H6: Mortality. We will compare NV and C participants on rates, ages, and causes of death.

The interpretation of outcomes specified in H1-6 will take into consideration the presence of existing disease and disabilities, based upon interviews, records of medication, diagnoses, and hospitalization records.

Approach to Specific Aim Two (Examine Moderators of Intervention Effects)

As elaborated below, we will examine all outcomes in this study in statistical models that employ sex of offspring as a classification factor and maternal psychological resources cross-classified with Treatment condition (NV-C). We have hypothesized (H7) that intervention effects (H1-5) will be more pronounced among females and mothers who gave birth to females, so analyses of NV-C differences will focus on these groups. We have elaborated methods to address this aim under the statistical methods and models below.

Approach to Specific Aim Three (Explore Mediators of NV Effects)

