The primary analyses will make use of general linear model methods and their extensions.⁸⁹⁻⁹⁴ The focus will be on (1) full model specification to account for all sources of variation, and full examination of interactions among model factors, including examination of homogeneity of regressions to understand interactions between classification effects and covariates; (2) generalized models to analyze dichotomous outcomes with binomial error distributions and count data assumed to have negative binomial distributions; (3) generalized linear mixed models (including repeated measures and growth-curve models) to account for correlated data and to examine differences in change over time; (4) semiparametric methods to model relations between variables without requiring a specific functional form;⁹⁵ (5) survival analyses including Kaplan-Meier, competing risks and Cox hazard models;⁹⁶⁻⁹⁹ (6) mediation analyses using structural equation models to examine causal processes, including the direct and indirect effects of treatment on outcomes.^{100,101}

The primary classification factors for examination in our models, as determined by our hypotheses and earlier work, include treatments (Control vs. Nurse Visited - T), maternal psychological resources (low versus high based on a median split – P), sex of offspring (S), and follow-up time (A) for outcomes assessed at multiple time points (e.g. obesity) – T|P|S and T|P|S|A. Covariates will be selected using a post-double-selection lasso (least absolute shrinkage and selection operator) procedure.¹⁰²⁻¹⁰⁴ This procedure will select covariates that are most related to intervention status (i.e. differences at randomization) or related to the dependent variable. Candidate covariates will include an index of household poverty, obesity, and maternal

pre-pregnancy BMI.

Statistical Power/Smallest Detectable Differences for Proposed Follow-Up

Given that sample size is fixed, we show below calculations of the smallest detectable treatment-control differences for the 29-year follow-up. Calculations for representative outcomes were carried out with the following assumptions: a Type I error of .05, Type II error of .20 (power of .80), 2-tailed tests, 10 percent of the variance accounted for by other terms in the model for normally distributed variables and N=600. Disproportionate sample sizes in Control and Nurse-Visited groups are taken into account.

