relationships, family economic resources, and hypertension at 12 and 18 years postpartum. H9: NV effects on offspring outcomes (H1-6) will be mediated, in part, by NV effects on prenatal health behaviors, preterm delivery, PIH, breast feeding, screen time at age 12, improved partner relationships, family economic resources through age 18, and obesity and prehypertension at ages 12 and 18. Tests of mediation will follow the empirical and theoretical model shown in Figures 1 and 2. We will employ mediation analyses using structural equation models to examine causal processes, including the direct and indirect effects of treatment on outcomes.^{100,101} To illustrate, we have hypothesized that NV will have an indirect effect on maternal arterial stiffness through its effect on PIH, preterm delivery, and the count of short inter-pregnancy intervals. To test one aspect of this hypothesis, we will regress maternal arterial stiffness on the count of closely spaced subsequent children (child density) within the control group; we also will regress child density on the treatment contrast. If the paths from the control sample to child density and from density to arterial stiffness are both significant, we will have met the joint significance test criterion. We will next calculate the indirect effect, based on these same two path coefficients, and compare the resultant z' to Mackinnon's table of critical values. If the z' is equal to or higher than the appropriate critical value, we will conclude that density of subsequent children mediates the effect of nurse visitation on maternal arterial stiffness. We will use this approach for each hypothesized mediator separately and jointly to develop a map of mediation.

Challenges in the Conduct of This Work

Missing Data. Missing data in this trial have been remarkably low. We are sensitive to the potential pitfalls of analyzing only cases with complete data.¹⁰⁵ We have complete data on all relevant background characteristics, which we will examine to address potential attrition bias. We also will compare our analyses to the same analyses employing inverse proportional weighting. We will perform sensitivity analyses to ensure that results are similar under various assumptions. We will determine whether imputation is valid and has sufficient added value with our data to justify the complexity involved in reporting these analyses.

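### The H8–H9 mediation rule concludes mediation on statistical thresholds alone, although its mediator–outcome path is an observational regression among controls with no stated confounding control

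*Combined protocol and SAP*

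**What the plan says.** The rule stands under Tests of Hypotheses, in the text on Hypotheses 8 and 9. It is illustrated with birth spacing and arterial stiffness:

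- **Mediator–outcome path:** "we will regress maternal arterial stiffness on the count of closely spaced subsequent children (child density) within the control group".
- **Treatment–mediator path:** child density is regressed on the treatment contrast.
- **Decision:** both paths must be significant, and z' is then compared with a published table of critical values. If it passes, "we will conclude that density of subsequent children mediates the effect of nurse visitation on maternal arterial stiffness".
- **Scope:** "We will use this approach for each hypothesized mediator separately and jointly to develop a map of mediation".

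No covariate is named for either path. The one statement on sensitivity analysis, "We will perform sensitivity analyses to ensure that results are similar under various assumptions", stands under Missing Data.

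Two general passages could bear on the point. Approach to Specific Aim Two says "we will examine all outcomes in this study in statistical models that employ sex of offspring as a classification factor and maternal psychological resources" will be used. Statistical Models and Methods of Analysis, which also lists mediation by structural equation models, plans a post-double-selection lasso: "This procedure will select covariates that are most related to intervention status (i.e. differences at randomization) or related to the dependent variable". It adds: "Candidate covariates will include an index of household poverty", and maternal pre-pregnancy BMI is also a candidate. The H8–H9 text refers to neither passage. Under Tests of Hypotheses, the lasso covariates are attached to the models for H1–5.

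**The concern.** Women were randomised to nurse visiting, not to birth spacing. The mediator–outcome regression compares control mothers according to their own later childbearing, so anything that influences both spacing and vascular health can produce an association without any effect of spacing. If treatment also shifts the mediator, both parts of the rule can then be met although the mediator does nothing.

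The premise is not remote. Table 3 reports a treatment effect on closely spaced births (0.51 against 0.34, p=.019), and the section on maternal pathways describes economic adversity as a strong predictor of cardiovascular risk in women. That adversity also affects birth spacing is plausible, but the documents do not say so.

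At stake is the set of mediation statements under Aim 3. The treatment comparisons in H1–H6 do not use this rule.

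**Working it through.** **Plan's own figures.** The documents give no operating characteristic for the mediation rule. The nearest stated figure is the detectable difference in Table 7, which confirms the sample split used here. With N=600 split 514:228, the groups are 600×514/742 = 415.6 controls and 184.4 nurse-visited. Then (1.960+0.842)×√0.90×√(1/415.6+1/184.4) = 0.235 SD (stated .24). At N=300 the result is 0.333 (stated .33). Both agree within rounding.

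**Inputs from the plan.** 416 controls, 184 nurse-visited, two-sided .05 on each path, mediator–outcome path in controls only, treatment path at p=.019 (z=2.346).

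**Assumptions.** True mediator effect zero; standardised normal mediator and outcome; one unadjusted shared cause with the loadings shown. The documents give no confounder strength and do not reproduce the z' table.

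**Step 1: treatment path.** If the true effect equals the reported one, the path is significant with probability Φ(2.346−1.96) ≈ .65.

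**Step 2: mediator–outcome path.** The induced correlation r is the product of the two loadings. The expected z is atanh(r)×√(416−3).

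- Loadings .2/.2: r=.04, z=0.81, significant in about 12.9%.
- Loadings .3/.3: r=.09, z=1.83, significant in about 45.0%.

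**Step 3: joint significance.** .65×.129 = .084 and .65×.450 = .293. Simulation with 20,000 runs per setting gives .082 and .286.

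**Step 4: z' condition.** z' = |z_a z_b|/√(z_a²+z_b²). Two paths each at 1.96 already give 1.96/√2 = 1.39. A cut-off near 1 therefore never binds (.98 is the 95th percentile of |z'| when both paths are zero), and the rule reduces to joint significance. A cut-off of 1.96 does bind.

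| Loadings (mediator/outcome) | Joint significance alone | z' ≥ 1.96 |
|---|---|---|
| No shared cause | 3.2% | 0.6% |
| .2/.2 | 8.2% | 1.9% |
| .3/.3 | 28.6% | 11.3% |
| .3/.4 | 44.8% | 22.2% |
| .4/.4 | 59.0% | 38.6% |
| Any of these four, shared cause adjusted | 3.0–3.4% | 0.5–0.7% |

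**Step 5: limits of the problem.** If treatment does not move the mediator, the rule is met in 0.7%, 2.3%, 3.5% and 4.5% across the four loadings.

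**Step 6: if the lasso applies.** With the shared cause measured and among 30 assumed candidates, selection on treatment and outcome brings all four settings to 3.1–3.4%. It can miss a cause tied strongly to the mediator and weakly to the outcome: 9.5% at .5/.15 and 13.7% at .6/.12 (unadjusted 21.5% and 20.2%). When selection also uses the mediator, these fall to 3.0% and 3.4%.

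**Cross-check with a count mediator.** With Poisson means .51 and .34 and joint significance only, a shared cause with a log-rate effect of .3 and an outcome loading of .3 (induced correlation about .06) gives 21% unadjusted and 4% adjusted.

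**The case against.** The strongest reply is that the H8–H9 text is a worked illustration of one aspect of a larger structural equation analysis. That analysis is to follow Figures 1 and 2, which are not visible in the text available, and mediators are also tested jointly. Mediation is listed in the same methods section that sets out the lasso without restriction, and sex and psychological resources are planned for all outcomes. On that reading the path may be adjusted, and if the shared cause is a candidate covariate the excess largely disappears. This stands as a possible intention. It does not close the gap: the rule does not invoke those covariates, the lasso as described does not select on the mediator, and no covariate set deals with unmeasured causes.

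A reader might infer more than the documents support:

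- **That the conclusion is unconditional.** It is conditional on significance and on z'. What is missing is a causal condition.
- **That the plan has no covariate adjustment for mediation.** The general text may supply some.
- **That false mediation claims are likely in half of cases.** The 45–59% rows need an outcome loading of .4, so that one cause explains .4² = 16% of outcome variance. The power section assumes 10% for all other model terms together. That does not bound unmeasured causes, but it makes these rows strong assumptions.
- **That the main results are at risk.** H1–H6 do not depend on this rule, and Aim 3 is described as exploring mediators.

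**Conclusion.** The point holds as a modest one. The rule declares mediation on statistical thresholds alone, with an observational mediator–outcome path for which it names no covariates. No assumption or sensitivity analysis for unmeasured mediator–outcome confounding is stated anywhere in the documents.

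For moderate shared causes (loadings .2 to .3), the rule would be met wrongly in about 8–29% of runs by joint significance, or 2–11% at a z' cut-off of 1.96. Adjustment brings this to about 3% or 0.5%. These are illustrations under assumed confounder strengths and a true treatment effect on the mediator equal to that in Table 3; they are not estimates for this trial. At .2/.2 with the stricter cut-off the problem is negligible. The consequence is confined to the exploratory mediation findings.

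**What to change.** In the H8–H9 text:

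1. State that the mediator–outcome model adjusts for maternal psychological resources, offspring sex and the baseline lasso candidates (household poverty index, pre-pregnancy BMI). Any lasso used there should select on the mediator as well as the outcome. Neighbourhood adversity at registration may be added where it has been scored, but the documents plan it only for mortality.
2. Add a sensitivity analysis for unmeasured mediator–outcome confounding.
3. Replace the concluding sentence with wording such as: the result is consistent with mediation, assuming no unmeasured mediator–outcome confounding.
4. As an editorial correction, amend "If the paths from the control sample to child density and from density to arterial stiffness are both significant" so that the first path runs from treatment, matching the regression described just before it.

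The cost is some SAP wording, a little more analysis and more cautious mediation conclusions. The covariates in item 1, apart from neighbourhood adversity, are already in the analysis plan. Sample size and power do not change.
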